### ***Testing visits***

Clinical assessments (blood draw and vascular health measurements) will be conducted at baseline (prior to study start) and at the end of each of the three 4-week supplementation periods, on two consecutive days. Each day of testing will be performed following an overnight fast (12 hours with no food or drink except water). Testing will be performed at the University of Arizona Collaboratory Research Center and the Clinical and Translational Science Research Center (CATS). At each visit, participants will be weighed and their vital signs (temperature and blood pressure) will be measured. Vascular health measures (i.e., central BP and indices of arterial stiffness) will be performed on Day 1, prior to blood sampling. The fasting lipid profile will be measured on both days to account for natural variation in these values. Blood will be processed according to standard procedures for serum lipids and subsequent laboratory analysis of oxidative stress/inflammatory biomarkers (see following experimental endpoints).

### ***Lipid profile and other blood markers of Cardiovascular Disease risk***

Whole blood will be drawn into serum separator tubes, allowed to clot, and centrifuged. Total cholesterol and triglycerides will be determined by enzymatic procedures (Sonoran Quest). HDL-C will be estimated according to the modified heparin-manganese procedure (CV < 2%). LDL-C will be calculated using the Friedewald equation:  $LDL-C = TC - (HDL-C + TG/5)$  except in cases where triglyceride values exceed recommended ranges. In these cases a direct LDL-C assay will be done that measures LDL-C concentration using a chromogenic reaction after removal of all non-LDL-C (N-geneous LDL-ST-C, Sonoran Quest). The between run CV of this assay is less than 3%. Insulin will be measured by radioimmunoassay (Sonoran Quest). Glucose will be determined by Spectrophotometry procedures (Sonoran Quest).

### ***Vascular function measures***

Vascular function, in terms of central blood pressure and arterial stiffness indices, will be assessed using the SphygmoCor System pulse waveform analysis (AtCor Medical, Sydney, Australia). Measurements will be taken in a quiet, temperature-controlled, dimly lit room.

- **Pulse Wave Analysis (PWA): Aortic Blood Pressure and Augmentation Index**

Following a 5 minute seated rest, aortic (central) blood pressure and wave reflection characteristics (augmentation index) will be derived from brachial pressure waveforms using a validated generalized transfer function. On each test day, three PWA measures will be taken, following JNC 7 blood pressure guidelines, with 1 minute in between each reading. The last 2 PWA results will be averaged and used for analysis.

- **Pulse Wave Velocity (PWV): Aortic Stiffness**

Aortic stiffness will be assessed by carotid-femoral pulse wave velocity (PWV). Carotid and femoral arterial pressure waveforms will be measured simultaneously via an applanation tonometry sensor manually held in place above the right common carotid artery and a blood pressure cuff placed on the right common femoral artery. PWV will subsequently be calculated by dividing the linear distance between the carotid and femoral sites by the transit time using the SphygmoCor system (AtCor Medical, Sydney Australia). On each test day, three PWV measurements will be obtained in the supine position, and the last two will be averaged for analysis.

### ***Blood markers of inflammation***

Serum hs-CRP will be measured by latex-enhanced immunonephelometry (Sonoran Quest).

### ***Gut microbiome analysis***

High-throughput sequencing of the 16S rRNA gene will be used to profile the bacterial community. This will identify and quantify dynamic changes in bacterial taxa present within the gut microbiome following supplementation. Stool samples will be collected at baseline and following each 4 supplementation period. Bacterial DNA will be extracted using the MoBio PowerFecal DNA Isolation Kit and the Qiagen Microbiome Kit will be used to eliminate host DNA. PCR amplification of the v3-v4 region of the 16S rRNA gene will be performed using the Illumina-tag PCR protocol. Purified library pools will be sequenced using Illumina MiSeq V3 500 cycle chemistry.

### ***Statistical Analysis***

Statistical analyses for blood markers of CVD risk, markers of inflammation, and vascular function measurements will be performed using SAS (version 9.4; SAS Institute). Treatment comparisons will be made between each of the supplementation periods. The mixed models procedure (PROC MIXED) will be used to test the effects of supplementation, period, and their interaction on outcome measures. Selection of model covariance structures will be based on optimizing fit statistics (evaluated as lowest Bayesian Information Criterion). Mixed models for endpoint means and change scores will be evaluated. Change scores will be calculated by subtracting baseline values from endpoint values. Means will be reported as least-squares means  $\pm$  SEM. Baseline values will be included as covariates. For all tests,  $\alpha$  will be set at 0.05.

For gut microbiome analyses, microbial DNA sequences will be quality filtered at an expected error of less than 0.5% using USEARCH v7. After quality filtering, reads will be analyzed using QIIME 1.9.0. An Operational Taxonomic Unit (OTU) table will then undergo cumulative sum scaling (CSS) normalization prior to beta diversity and alpha diversity analyses. Principal coordinates analysis (PCoA) plots and ANOSIM tests for significance will be performed using a weighted unifracs distance matrix. Linear Discriminant Analysis (LDA) effect size (LEfSe) will be used to identify potential differences in the microbial community following each intervention. Exploratory Spearman rank correlations will be performed between bacterial taxa and other physiological measurements (e.g., LDL-C, blood pressure, and inflammatory markers) to identify potential microbial signatures associated with CVD risk reduction.

The Principal investigator, Co-Principal Investigator and Authorizing Official for the University of Arizona, have reviewed and approved the proposal for consideration of funding.

  
[name] 7/17/17  
Date

  
[name] 7/17/17  
Date

 for [name], Senior VP for Research 7/26/17  
Authorizing Official for the University of Arizona Date

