**SUMMARY**

Dietary interventions designed to reduce cardiovascular disease (CVD) risk by increasing consumption of particular health-promoting foods (e.g., strawberries) generally target blood pressure and LDL-C—the two endpoints recognized by the FDA for a cardiovascular health claim; however, CVD risk reduction may also be achieved via changes in emerging endpoints such as the gut microbiome. Previous research suggests that strawberries have the potential to reduce LDL-C, but it remains unclear whether there is a dose-response relationship. Moreover, few studies have evaluated effects on vascular health or characterized changes in the gut microbiome following daily strawberry consumption. Additionally, previous studies have largely been conducted among Caucasian populations. Given the demographics of the US, it is important to evaluate effects in study populations that include ethnicities that may have higher risk of type 2 diabetes and/or other CVD risk factors, such as Hispanics. We propose to examine the effects of 4 weeks of supplementation with two doses of freeze dried strawberry powder (low dose: 13 g/d and high dose: 40 g/d) on: 1) LDL-C and blood pressure; 2) gut microbiome profile; and 3) other CVD and type 2 diabetes risk factors, including glucose, insulin, and inflammatory markers. We will enroll overweight (BMI 25-36 kg/m^2) but otherwise healthy adults with moderately elevated LDL-C (>3.0 mmol/L) and/or prehypertension (120-159/80-99 mm Hg). This will optimize the potential for observing significant benefits on these outcomes. We will recruit 50 eligible participants with the expectation that at least 40 will complete the study. The placebo-controlled, crossover study design will allow for a direct comparison of dose-response within the same participant. We anticipate that the bioactive components of strawberries will reduce LDL-C and blood pressure, and modify the gut microbiome, with greater changes on the high dose. There is preliminary evidence that polyphenol-rich foods can modify gut microbiota profiles, but this would be the first study to characterize the effects of daily strawberry consumption. We are uniquely placed at the University of Arizona to enroll a larger percentage of Hispanic participants, who are often under-represented in clinical nutritional research. Results from the proposed study could strengthen the evidence for a cardiovascular health claim for strawberries and draw greater attention to strawberries as a phytonutrient-rich food that can lower LDL-C and blood pressure, and modify the gut microbiome.

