### ***Experimental Design***

We propose to conduct a 3-period randomized crossover dose-response study to evaluate the effect of freeze dried strawberries on LDL-C, vascular function, and the gut microbiome. Participants will be randomly assigned to three supplementation periods: 1) low-dose freeze dried strawberry powder (13 g/d); 2) high-dose freeze dried strawberry powder (40 g/d); and 3) a placebo powder. Each powder will be provided for 4-6 weeks, separated by a 2-week washout period/compliance break between treatment periods. Therefore, end of treatment values will be separated by at least 6 weeks (4-6 week supplementation period + 2 week break), which is sufficient for endpoints to stabilize. Total study time for participants will be approximately 16-20 weeks.

The high dose (40 g/d) will act as a proof of principle dose and is equivalent to the amount consumed acutely in our previous postprandial study. The 13 g/d low dose is equivalent to approximately 1 serving of fresh strawberries per day and represents a quantity that is easily achievable under free-living conditions. The use of both a low and high dose of freeze dried strawberry powder will allow us to investigate potential dose-response effects and determine whether benefits are achievable with smaller quantities. During each supplementation period, participants will be instructed to consume one package of study powder per day. Participants will be instructed to consume study powders in between meals and mixed with a water-based beverage to minimize the chance of other foods (e.g., dairy proteins) inhibiting absorption of strawberry bioactives. To maintain blinding and consistency in powder volume across

supplementation periods, freeze dried strawberry powder and placebo powder will be combined to achieve the low dose. For the proposed study population size (n = 50), this will require 2100 packages of each powder type (placebo, low-dose, and high-dose), provided in individually portioned packages, with the following contents:

- Placebo powder (40 g packages)
- Low-dose strawberry supplementation (40 g packages, consisting of 13 g freeze dried strawberry powder + 27 g placebo powder)
- High-dose strawberry supplementation (40 g packages, consisting of 40 g freeze dried strawberry powder)

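### The plan does not say that the treatment contrasts exclude the supplementation-by-period interaction, and it names no balanced orders: a small, avoidable precision loss and a test that cannot be interpreted

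*Combined protocol and SAP*

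**What the plan says.** Experimental Design describes the trial: "We propose to conduct a 3-period randomized crossover dose-response study". On allocation it says "Participants will be randomly assigned to three supplementation periods". It lists no set of orders, no Latin or Williams square, and no blocking. Treatment periods are "separated by a 2-week washout period/compliance break between treatment periods". The Summary gives the numbers: "We will recruit 50 eligible participants with the expectation that at least 40 will complete the study".

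In Statistical Analysis, the mixed model "will be used to test the effects of supplementation, period, and their interaction on outcome measures". A separate sentence says "Treatment comparisons will be made between each of the supplementation periods", and another says "Means will be reported as least-squares means". Baseline is a covariate, the covariance structure is chosen by lowest BIC, and alpha "will be set at 0.05". No sequence or carryover term is named. The plan names no reduced model and gives no rule for what follows a significant interaction.

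**The concern.** The contrasts of each dose with placebo, and of high with low dose, are the trial's answer. The natural reading is that they are differences of least-squares means from the one model stated, which includes the interaction. Under that model each treatment mean is the equal-weight average of its three period-specific means. If the nine treatment-by-period cells are unequally filled, thin cells get full weight and some of the comparison is made between persons rather than within them. The standard error is then larger than the same data would give without the term.

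The interaction test is also hard to read. In a three-period crossover the term shares information with sequence differences and with carryover. A small p-value would not show which of these, or a real change of effect over time, produced it. The plan does not say what would then happen to the main contrasts.

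**Working it through.** The plan gives no SD, effect size, power or precision figure, so there is nothing of its own to reproduce.

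**Inputs.** From the documents: three treatments, three periods, 50 recruited, at least 40 completing. Assumed: a random participant effect (compound symmetry), two-sided testing, within-person SD 10, between-person SD 9 to 25, and 10 of 50 leaving early. The lower SD allows for the baseline covariate. If one baseline shares SDs of 25 and 10, the residual between-person SD is √(25² × 10² / (25² + 10²)) = √86.2 ≈ 9.3. In correlation terms, 25²/(25² + 10²) = 0.86 and 86.2/(86.2 + 100) = 0.46. Runs at correlations of 0.5 to 0.9 therefore cover nearly all of this range.

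**Step 1: balanced orders, complete data.** All nine cells have equal size, so the equal-weight average is also the additive-model estimate. The generalised least squares variance of a treatment contrast with the interaction, divided by that without it, is 1.000 for both three and six orders (checked at n = 42 and 48). Since 50 = 8 × 6 + 2, blocks of six leave two participants over, and the SE cost is about 0.1%. The 4 degrees of freedom spent barely matter. With 40 completers the denominator df are 120 − 40 − 2 − 2 = 76 without the term and 72 with it, so the critical t moves from 1.992 to 1.993.

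**Step 2: dropout and unrestricted orders.** The SE cost is √(variance ratio) − 1. Six orders, 50 randomised, 10 leaving early:

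| Allocation | Correlation | Mean variance ratio | Mean SE cost | 95th percentile ratio | SE cost there |
|---|---|---|---|---|---|
| Balanced | 0.5-0.9 | 1.012 | 0.6% | 1.02 | about 1% |
| Unrestricted | 0.5 | 1.047 | 2.3% | 1.112 | 5.5% |
| Unrestricted | 0.8 | 1.055 | 2.7% | 1.125 | 6.1% |
| Unrestricted | 0.9 | 1.056 | 2.8% | 1.135 | 6.6% |

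With SDs of 25 and 10, and dropouts split equally between the end of period 1 and the end of period 2, the cost was 2.6-2.7% on average and 6.6-7.0% at the 95th percentile. With the between-person SD at 9.3 the mean was 2.2%. I put the range at 2-3% on average and 5.5-8% at the 95th percentile. The top of the second range leaves room for simulation error in a tail percentile.

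**Step 3: what this means for power.** For a test with 80% power (a reference value, not the plan's), a variance ratio of 1.05 gives 78.1% and a ratio of 1.11 gives 75.8%. The effective number of completers falls from 40 to 40/1.05 = 38.1 and to 40/1.11 = 36.0.

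**Step 4: does the term protect against carryover?** Suppose the high dose leaves one unit of effect in the next period. With all six orders used equally, placebo directly follows the high dose in 2 of 6 orders, and the high dose never follows itself. High minus placebo is biased by −2/6 = −0.33. In the three-order Latin square placebo-low-high, low-high-placebo, high-placebo-low, placebo follows the high dose in 2 of 3 orders, and the bias is −0.67. Both figures are the same with and without the interaction.

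**Step 5: what does the interaction measure?** It has 4 df.
- Three-order Latin square: 2 df lie wholly between sequences. The other 2 coincide exactly with first-order carryover, and no separate carryover df remain.
- All six orders: all 4 df can be estimated within persons, at efficiency 0.5, so half their information lies between sequences. The term covers 25% of the adjusted carryover space, and 2 carryover df remain separately estimable.

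**The case against.** The strongest reply is that the plan says the interaction will be tested, not that it stays in the model when treatments are compared. If it is tested and then dropped, the precision loss disappears. That stands: retaining the term is the natural reading, but it is not stated. Naming the final model settles the matter either way.

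Second, silence on blocking does not show that allocation is unrestricted. That also stands. The 2-3% figure applies only if it is, and with blocked allocation to six orders the cost is at most about 0.6% on average. A reader might infer that the interaction costs precision in itself. Step 1 shows that it does not: the loss needs unbalanced orders or incomplete data.

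Third, a reader might infer that the term is aliased outright with sequence and carryover. That is true only for a three-order Latin square, and the documents do not say which orders are used. With all six orders the mixing is partial. The test can still flag a departure from additivity, although it cannot identify the cause.

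What the reply does not reach is that the interaction brings no benefit to the contrasts, and that the plan leaves both the final model and the use of the test undefined.

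**Conclusion.** The point holds as a minor, cost-free improvement. If the contrasts come from the stated model, the interaction adds between almost nothing (balanced orders) and about 2-3% on average (unrestricted orders, 10 of 50 leaving) to their standard error, with roughly 5.5-8% at the 95th percentile. These sizes rest on assumed SDs, compound symmetry and assumed dropout. Since the plan expects at least 40 completers, 10 dropouts is the upper end of its own expectation.

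The more lasting defect is interpretive: a significant interaction could not be assigned to a changing effect, and no rule says what would follow. A reader might go further and conclude that the treatment contrasts are biased or invalid because of the term. The documents do not support that. Any carryover bias is the same with or without it, and no conclusion of the trial is shown to change.

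**What to change.** - Name the six treatment orders and allocate participants to them in blocks.
- Pre-specify that all treatment contrasts come from the model with supplementation, period, baseline and a random participant effect.
- Fit the supplementation-by-period interaction once, as a separate descriptive check, and state that its result does not alter the primary contrasts.

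This costs a randomisation list and a few sentences, with no new data. If randomisation has already taken place, the model change alone still applies, and the orders actually used should be reported.

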### **Specific Aims**

1. To determine whether 4 weeks of freeze dried strawberry consumption improves the lipid profile (primarily LDL-C, as well as total cholesterol, HDL-C, and triglycerides) and other CVD risk factors (i.e., glucose, insulin, and inflammatory markers).
2. To determine whether 4 weeks of freeze dried strawberry consumption improves vascular function, in terms of resting brachial and central blood pressure and arterial stiffness indices (i.e., augmentation index and pulse wave velocity).
3. To identify changes in the composition of the gut microbiome following 4 weeks of freeze dried strawberry consumption.

4. To determine whether there is a dose-response effect with greater improvements achieved following high dose (40 g/d) supplementation.

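### CSS before alpha diversity helps none of the common indices: it leaves richness tied to read depth, collapses Chao1 to observed OTUs, and distorts Shannon if the output is logged

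*Combined protocol and SAP*

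**What the plan says.** The microbiome paragraph of Statistical Analysis sends quality-filtered reads to QIIME ("After quality filtering, reads will be analyzed using QIIME 1.9.0") and then prescribes a single normalisation for both kinds of diversity: "An Operational Taxonomic Unit (OTU) table will then undergo cumulative sum scaling (CSS) normalization prior to beta diversity and alpha diversity analyses". For beta diversity the plan goes on to name a distance and a test: "Principal coordinates analysis (PCoA) plots and ANOSIM tests for significance will be performed using a weighted unifracs distance matrix". For alpha diversity it names no index, no test, no rarefaction depth, no minimum read count and no depth covariate.

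The Gut microbiome analysis section names the sequencing chemistry ("Purified library pools will be sequenced using Illumina MiSeq V3 500 cycle chemistry") but gives no target or expected reads per sample. Stool is collected at baseline and after each supplementation period. The microbiome is the subject of Aim 3: "To identify changes in the composition of the gut microbiome following 4 weeks of freeze dried strawberry consumption".

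**The concern.** Samples in one sequencing run do not all receive the same number of reads, and a deeper sample shows more rare taxa even when the community is the same. An alpha-diversity analysis therefore needs some way of making samples comparable in depth. CSS is the only step in the plan that could do this. If it does not, a richness-type result carries depth variation as extra noise, and the stated normalisation gives false reassurance that depth has been dealt with. At stake is the alpha-diversity part of Aim 3. LDL-C, blood pressure and the other blood and vascular outcomes are not affected.

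**Working it through.** The plan gives no alpha-diversity figure to reproduce. Step 1 is algebra. The numbers in steps 2 to 4 come from simulations whose inputs (community shape, read depth, depth spread, within-person variation, effect size) are all assumed. Only the 40 completers come from the plan (Summary).

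**1. What CSS does.** For sample j, CSS replaces count x by y = c·x/s, where s > 0 is the sum of that sample's counts up to a chosen quantile and c is a fixed scale.

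- *Observed OTUs* = number of x > 0. Since y > 0 exactly when x > 0, the value is identical before and after, logged as log2(y+1) or not.
- *Chao1* = S_obs + f1(f1−1)/(2(f2+1)), where f1 and f2 are the numbers of OTUs with counts of exactly 1 and 2. Scaled values are generally neither, so f1 and f2 go to about 0 and Chao1 becomes S_obs.
- *Shannon and Simpson* depend on p = x/Σx. The factor c/s cancels, so unlogged CSS leaves them unchanged. A log transform does not cancel.

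**2. The algebra in numbers.** Assumed community of 600 OTUs with lognormal abundances:

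| Reads | Observed OTUs, before CSS | Observed OTUs, after CSS |
|---|---|---|
| 5,000 | 368 | 368 |
| 20,000 | 489 | 489 |
| 80,000 | 560 | 560 |

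At 20,000 reads Chao1 falls from 538 to 489, which is observed OTUs. Shannon is unchanged by unlogged CSS; logged, it goes from 4.56 to 6.05.

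A second assumed community (800 OTUs, abundance log-SD 2.5) agrees. At 5,000 reads the mean f1 is 109.2 and the mean f2 is 49.0. Putting these in gives 324.5 + 109.2 × 108.2/(2 × 50.0) ≈ 443 (446 when averaged over replicates), against 324 after CSS. From 5,000 to 80,000 reads, raw Shannon moves only from 3.935 to 4.025, while logged-CSS Shannon goes from 5.68 to 6.23.

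**3. Are integer counts alone enough?** No. In the 800-OTU community, Chao1 on integer counts still rises from 446 at 5,000 reads to 691 at 80,000, and observed OTUs rise from 324 to 624, exactly as under CSS. Rarefied to 5,000 reads, observed OTUs stay at 324 to 330 and Chao1 at 446 to 450 whatever the original depth.

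**4. Noise or bias, and how much.** Simulated crossover: 40 participants, three periods in random order, mean 20,000 reads, depth unrelated to treatment, observed OTUs as the index. The table shows the paired SD of high dose minus placebo by log-SD of depth. In brackets is the multiple of participants needed, (SD/SD at equal depth)².

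| Within-person variation | 0 | 0.1 | 0.3 | 0.5 |
|---|---|---|---|---|
| Low | 12.6 | 14.0 (1.2) | 23.5 (3.5) | 36.4 (8.3) |
| Medium | 23.5 | 24.2 (1.06) | 30.6 (1.7) | 41.1 (3.1) |
| High | 47.4 | 47.8 (1.02) | 51.0 (1.16) | 57.5 (1.47) |

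Closed-form check: SD = √(SD0² + 2(s·d)²), with s = 43 OTUs per log unit of depth and d the log-SD of depth. Medium case, d = 0.3: √(23.5² + 2 × 12.9²) = √885.1 = 29.8, against 30.6 simulated. Low case, d = 0.5: √(12.6² + 2 × 21.5²) = √1083.3 = 32.9, or (32.9/12.6)² = 6.8 times, against 8.3 simulated. The top-right corner is therefore the least secure figure.

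With no true effect, false positives on CSS data were 4.4 to 6.1% over the 12 settings, and the mean error was at most 0.22 OTU: noise, not bias. Power for an assumed effect of 15 more OTUs present, at depth log-SD 0 and then 0.3, was 82.1% then 56.2% in the medium case and 29.7% then 24.3% in the high-variation case (Monte Carlo SE at most 1.3 points). At log-SD 0.3, log depth as a covariate gave 79.9% and 26.3%; rarefying to 8,000 reads gave 74.5% and 25.7%.

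Bias appears only if depth itself differs between conditions. In a separate simulation of 40 pairs of identical communities, false positives on CSS data were 4.5, 18.5, 63 and 97.5% at depth ratios of 1.0, 1.1, 1.25 and 1.5, against 3.5 to 4.5% after rarefying (200 runs each).

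**The case against.** The strongest reply is that the harm is hypothetical. The plan says only "prior to beta diversity and alpha diversity analyses" and mentions neither Chao1 nor observed OTUs; with Shannon or Simpson on unlogged output, nothing changes. This stands, and it makes the harm conditional. It does not rescue the step, which improves none of the four indices under either reading of CSS. Whether the output is logged is not stated, so harm to Shannon cannot be excluded.

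A second reply is that the reach is small. Aim 3 concerns composition, for which weighted UniFrac with ANOSIM and LEfSe are named. This also stands and is why the point is minor.

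Three stronger readings are tempting, and the documents support none of them:

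- *That the treatment comparison is biased.* Order is randomised ("Participants will be randomly assigned to three supplementation periods"), and nothing indicates that depth differs by treatment. The documents do not say how samples are allocated to sequencing runs, so the 18.5 to 97.5% figures describe a condition to guard against, not one shown to exist.
- *That several times the participants would be needed.* The 8.3-fold figure takes the lowest assumed within-person variation together with the widest assumed depth spread, and the closed form gives 6.8 there.
- *That a covariate is better than rarefying.* The simulated gap partly reflects the choice of 8,000 reads when the mean was 20,000, and Chao1 was not in the power runs.

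Nor does the point endorse or criticise CSS for beta diversity. Unlogged scaling leaves a proportion-based distance unchanged, and that step is outside this point.

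**Conclusion.** The concern holds, conditionally, and is minor. That CSS leaves observed OTUs and their depth dependence intact is exact and rests on no assumption. The collapse of Chao1 follows from the loss of integer counts and appeared in the assumed communities. Shannon and Simpson are untouched if the output is unlogged; logging inflates Shannon and makes it rise with depth. The practical cost depends on an index the plan does not name and a depth spread it does not give. For observed OTUs under assumed inputs, it runs from about 2% more participants to several times as many. It falls on the precision of the alpha-diversity part of Aim 3. No bias is expected among the three powders unless read depth differs systematically between conditions.

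**What to change.** In the microbiome paragraph of Statistical Analysis:

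1. Remove alpha diversity from the CSS step and compute it from the un-normalised integer OTU counts.
2. Name the alpha index.
3. For any richness-type index (observed OTUs, Chao1), also handle read depth: either rarefy all samples to one common depth stated in advance, or include log read depth as a covariate in the treatment comparison.

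The cost is one changed step and two or three sentences, with no new data. Rarefying discards reads and may drop shallow samples; in the assumed runs at 8,000 reads it dropped 0.2% of samples at depth log-SD 0.3 and 5.7% at 0.5. The covariate keeps every sample but assumes richness is roughly linear in log depth. Either is acceptable if it is fixed before the data are seen.

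### ANOSIM and LEfSe are named for the microbiome without participant blocking or pairing, so in standard form they give up the crossover's within-person precision

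*Combined protocol and SAP*

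**What the plan says.** The Experimental Design section describes a "3-period randomized crossover dose-response study to evaluate the effect of freeze dried strawberries on LDL-C, vascular function, and the gut microbiome". The Summary gives the reason for that design: "The placebo-controlled, crossover study design will allow for a direct comparison of dose-response within the same participant". The Gut microbiome analysis section makes the stool data repeated within person: "Stool samples will be collected at baseline and following each 4 supplementation period". A completer therefore supplies four samples, three of them at the end of a treatment period. Specific Aim 3 is to identify compositional changes after supplementation.

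The Statistical Analysis section treats two groups of outcomes differently. The first paragraph opens with "Statistical analyses for blood markers of CVD risk, markers of inflammation, and vascular function measurements will be performed using SAS" and goes on to a mixed model with supplementation, period, their interaction and a baseline covariate. The second paragraph covers the microbiome. For overall composition: "Principal coordinates analysis (PCoA) plots and ANOSIM tests for significance will be performed using a weighted unifracs distance matrix". For individual taxa: "Linear Discriminant Analysis (LDA) effect size (LEfSe) will be used to identify potential differences in the microbial community following each intervention". It mentions no participant block, strata, restricted permutation, pairing or participant effect, and nothing elsewhere in the supplied text adds one.

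**The concern.** People differ from one another in gut flora, and a crossover is meant to remove those stable differences from the treatment comparison. ANOSIM with labels permuted freely over all samples does not remove them. Nor does LEfSe in standard form, which admits a taxon only if it passes an unpaired Kruskal-Wallis test. In both, variation between people stays in the reference distribution although it does not affect the within-person contrast.

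If the within-person correlation is positive, the tests reject too rarely under the null and generally lose power. A negative microbiome result could then come from the choice of test rather than from the strawberries. That matters for Aim 3 and for the stated purpose of the sequencing: "This will identify and quantify dynamic changes in bacterial taxa present within the gut microbiome following supplementation".

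**Working it through.** The plan gives no power, variance, correlation or effect size for the microbiome, so there is no figure of its own to reproduce. From the documents: three treatment conditions, alpha 0.05 (taken as two-sided), and 40 completers ("We will recruit 50 eligible participants with the expectation that at least 40 will complete the study"). Assumed: within-person correlation ρ of 0.1, 0.3, 0.5 or 0.7, and a shift in units of within-person SD at the high dose with half of it at the low dose. Only the three end-of-period samples are used.

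**1. One pairwise contrast, closed form.** With total variance 1, the true standard error of a within-person difference is √(2(1−ρ)/n); an unpaired test uses √(2/n). Set the effect so that the paired test has 80% power, that is (1.96 + 0.84) = 2.80 true standard errors. Then

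- unpaired power = Φ(2.80 − 1.96/√(1−ρ))
- unpaired null rejection = 2Φ(−1.96/√(1−ρ))

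The sample size cancels. Example at ρ = 0.5: 1.96/√0.5 = 2.77, so power = Φ(0.03) = 51% and null rejection = 2Φ(−2.77) = 0.6%.

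| ρ | 0.1 | 0.3 | 0.5 | 0.7 |
|---|---|---|---|---|
| Unpaired power, % (paired = 80) | 77 | 68 | 51 | 22 |
| Unpaired null rejection, % (nominal 5) | 3.9 | 1.9 | 0.6 | 0.03 |

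**2. ANOSIM on weighted UniFrac, simulated.** 1,000 data sets per cell and 199 permutations; 100 OTUs, 20 of them shifted, on random trees; 10,000 reads; CSS normalisation. Rejection rates in %:

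| Shift | Permutation | ρ = 0.1 | 0.3 | 0.5 | 0.7 |
|---|---|---|---|---|---|
| 0 (null) | free | 2.6 | 0.1 | 0 | 0 |
| 0 (null) | within participant | 5–6 | 5–6 | 5–6 | 5–6 |
| 0.5 | free | 33 | 7 | 0 | 0 |
| 0.5 | within participant | 51 | 43 | 42 | 27 |
| 0.7 | free | 76 | 34 | 3 | 0 |
| 0.7 | within participant | 88 | 81 | 77 | 63 |
| 0.9 | free | 97 | 78 | 26 | 1 |
| 0.9 | within participant | 99 | 99 | 97 | 89 |
| 1.2 | free | 100 | 99 | 85 | 16 |
| 1.2 | within participant | 99–100 | 99–100 | 99–100 | 99–100 |

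A check on 20 normal axes with Euclidean distance (5 shifted by 0.7) gives the same pattern: free 94, 59, 8 and 0%; within participant 96–98%.

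**3. One taxon, shift 0.7, unadjusted, 4,000 data sets.** Power in %:

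| Test | ρ = 0.1 | 0.3 | 0.5 | 0.7 |
|---|---|---|---|---|
| Kruskal-Wallis, three conditions | 74 | 59 | 39 | 11 |
| Friedman, three conditions | 63–66 | 63–66 | 63–66 | 63–66 |
| Rank-sum, high dose vs placebo | 84 | 75 | 59 | 31 |
| Signed-rank, high dose vs placebo | 84–86 | 84–86 | 84–86 | 84–86 |

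At ρ = 0.1 Friedman does worse than Kruskal-Wallis, and signed-rank about equals rank-sum.

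**4. Many taxa with false-discovery control.** 100 taxa × 3 contrasts, Benjamini-Hochberg at 5%, 500 data sets per cell, shift 0.9. Share of truly shifted taxa found for high dose vs placebo (last row: share passing the three-group gate), in %:

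| Method | ρ = 0.1 | 0.3 | 0.5 | 0.7 |
|---|---|---|---|---|
| Rank-sum, controlled | 65 | 42 | 11 | 1 |
| Signed-rank, controlled | 64 | 62 | 56 | 44 |
| Participant-effect model, controlled | 74 | 70 | 67 | 55 |
| Kruskal-Wallis gate, uncontrolled | 87 | 79 | 62 | 28 |

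The realised false discovery rate of the two paired methods was 1.7–4.9% over the simulated shifts. Without control they give about 15 false positives per 300 null tests (300 × 0.05). The uncontrolled gate passed 3.3, 1.6, 0.5 and 0.1 false taxa out of 80 unshifted. Its row is a three-group test beside a single contrast, so that comparison is only approximate.

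**Limits.** The tree and abundance model are assumed. No period effect or missing data were simulated. The full LEfSe procedure was not simulated; Kruskal-Wallis power at 0.05 is an upper limit for LEfSe run at that level.

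**The case against.** - **For ANOSIM this is silence, not error.** The plan does not say how labels are permuted, and blocked permutation fits its text. This stands. The ANOSIM losses apply only if permutation is free, so the request there is to state the blocking. It does not answer the LEfSe point, because the standard gate is unpaired.
- **This is efficiency on a non-primary aim.** The fault is conservative, and LDL-C and blood pressure already have a mixed model. LEfSe is worded as a search for potential differences, and the taxon correlations are labelled exploratory. This limits the priority. Still, ANOSIM is described as a test for significance, and Aim 3 is one of four stated aims.
- **This trial's loss is unknown.** True. At a correlation of 0.1 the ANOSIM loss is between 0 and 18 points, depending on effect size, and a single taxon gains little or nothing.
- **The taxon-level remedy can find fewer taxa.** Also true. False-discovery control is a separate matter from pairing. At shift 0.9 and correlations of 0.1 and 0.3, both controlled paired methods find fewer shifted taxa than the uncontrolled gate. At 0.5 the participant-effect model finds slightly more and signed-rank slightly fewer; at 0.7 both find more. With the same control applied to both, signed-rank is within a point of rank-sum at 0.1 and clearly better from 0.3 upward.

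**Conclusion.** The concern holds as an inexpensive improvement worth making. The design and sampling support within-person comparison of the microbiome, and the named analysis does not say that it will use it. The direction is certain for positive within-person correlation: conservative tests, with power generally lost and no excess of false positives.

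The size is conditional. For free-permutation ANOSIM the loss runs from 0–18 points at an assumed correlation of 0.1 to nearly all power at 0.7, where 0–1% remains for shifts up to 0.9 and 16% at 1.2. For a single taxon the loss is negligible at 0.1 and substantial from about 0.5. These figures rest on 40 completers, the assumed correlations and shifts, and the assumed abundance model. None of them estimates this trial's own loss.

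**What to change.** - **Overall composition:** run the weighted UniFrac test with permutations restricted within participant, either as blocked ANOSIM or as PERMANOVA with participant as strata, and say so. Only blocked ANOSIM was simulated here. State which samples enter; the figures above use the three end-of-period samples.
- **Taxa:** base inference on a test that uses the pairing, either a mixed model with a random participant effect or signed-rank contrasts between conditions. Keep LEfSe as a descriptive display.
- **Multiplicity, a separate decision:** state a false-discovery-rate control across taxa and contrasts. The price is the stricter threshold shown in step 4.
- **Optional, and not part of the fault:** include a period term, as the model for the other outcomes already does. It guards against bias if a period trend coincides with unbalanced sequences. Its benefit was not quantified.

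The cost is a few sentences and a little analysis code, with no new samples, visits or participants. The change should be made before the microbiome data are analysed.
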